### **1.1 Study Objectives and Endpoints**

Study TTI-621-01/C4961001 has four parts.

#### **1.1.1 Phase 1a Dose Escalation (Part 1)**

The primary objective of the escalation phase of the study is to characterize the safety profile and dose limiting toxicities (DLT) of TTI-621 in order to identify the MTD and/or the optimal dose in adult subjects with advanced relapsed or refractory lymphomas.

Primary endpoints are:

- Dose Limiting Toxicities (DLTs) at escalated doses of TTI-621
- Incidence and severity of AEs

DLT is defined for Phase 1a Dose Escalation (Part 1) as any of the following treatment-emergent events occurring during the DLT treatment/ observation period (including the predose tests on Day 22):

- Grade 4 thrombocytopenia
- Grade 3 thrombocytopenia with bleeding (with the exception of brief, easily-controlled epistaxis, mild gum bleeding or normal menses) or with any requirement for platelet transfusions
- Grade 4 anemia, unexplained by underlying disease
- Grade 4 neutropenia lasting more than 5 days
- Febrile neutropenia of any duration ( $ANC < 1.0 \times 10^9/L$ , fever  $> 38.5^{\circ}C$ )
- Grade 3 or higher non-hematologic toxicity except for alopecia and nausea controlled by medical management
- Grade 3 or 4 hemorrhage

- Grade 3 or 4 cytokine release syndrome

Secondary objectives include characterization of the pharmacokinetics (PK) of TTI-621, development of antidrug antibodies, and pharmacodynamics through various biomarker studies. (Analyses of PK/PDx data will take place outside Sarah Cannon Development Innovations.)

Secondary endpoints are:

- PK profile, PD, ADA

### **1.1.2 Phase 1b Dose Expansion (Parts 2 and 3)**

The primary objective of the expansion phase of the study is to further characterize the safety of TTI-621 in an expanded number of primary hematologic malignancies and selected solid tumors, and to evaluate the safety of individual subject TTI-621 dose intensification.

Primary endpoints are:

- Incidence and severity of AEs

Secondary objectives include additional characterization of PK, pharmacodynamics, and development of ADA; and to gain preliminary evidence of the antitumor activity of TTI-621 in subjects with a variety of hematologic malignancies and selected solid tumors. In addition, the safety of TTI-621 will be evaluated in combination with other anti-cancer agents.

Secondary endpoints are:

- PK profile, PD, ADA
- Overall response rate, duration of response, and progression-free survival
- Part 3: CTCL and PTCL: organ system overall response rate

### **1.1.3 Phase 1b Dose Optimization (Part 4)**

The primary objective of the dose optimization phase is to further evaluate the safety and tolerability of TTI-621 at dose levels higher than the initially recommended Phase 1b dose of 0.2 mg/kg (as determined during Phase 1a dose escalation) and the MTD will be re-assessed per revised DLT criteria following a 3+3 dose escalation schema. The DLT criteria are revised based on the totality of safety data collected thus far from the Phase 1a and 1b dose expansion phase of the study. The starting dose for this further dose evaluation will be the highest dose of TTI-621 evaluated (0.5 mg/kg) during Phase 1b dose expansion following dose intensification regimens permissible per protocol (Part 2 and Part 3).

Primary endpoints are:

- Dose Limiting Toxicities (DLTs) at escalated doses of TTI-621
- Incidence and severity of AEs

A DLT is defined in Phase 1b Dose Optimization (Part 4) as any of the following TEAEs that occur during the DLT period and that are considered at least possibly related to study treatment by the investigator. Note that any AEs for which the relationship to study treatment cannot be ruled out should be considered possibly related:

- Grade 4 thrombocytopenia ( $<25 \times 10^9/L$ ) lasting  $>72$  hours or a platelet count  $\leq 10 \times 10^9/L$  at any time
- $\geq$  Grade 3 thrombocytopenia with bleeding (except epistaxis or gingival bleeding that is less than 24 hours in duration and does not require medical intervention, or normal menses) or requiring platelet transfusions
- Grade 4 anemia, unexplained by underlying disease
- Grade 4 neutropenia lasting  $>72$  hours
- Grade 3 febrile neutropenia lasting  $>72$  hours
- Grade 4 febrile neutropenia
- Grade 3 or higher non-hematologic toxicity with the following exceptions:
  - Grade 3 nausea and/or vomiting lasting  $<72$  hours with standard supportive care
  - Transient Grade 3 fatigue lasting  $\leq 72$  hours
  - Transient asymptomatic Grade 3 laboratory abnormalities considered not clinically significant following agreement between investigators and the sponsor's medical monitor and that last  $<72$  hours with standard supportive care
- Other  $\geq$  Grade 2 TTI-621-related non-hematologic toxicities that, in the opinion of the investigator, require a dose reduction or discontinuation of TTI-621

Secondary objectives include characterization of the PK, PD, immunogenicity, and preliminary evidence of antitumor activity of TTI-621 in subjects with relapsed and/or refractory CTCL at higher dose levels of TTI-621.

Secondary endpoints are:

- PK profile, PD, ADA
- Overall response rate and duration of response
- CTCL: organ system overall response rate

## 1.2 Investigational Plan

### 1.2.1 Overall Study Design

The escalation and expansion phases will be conducted as a multicenter, open-label trial of single-agent TTI-621 and TTI-621 in combination with other therapies in subjects with relapsed or refractory hematologic malignancies and selected solid tumors; the study will be conducted in 4 parts. Neither randomization nor blinding will be utilized.

### 1.2.2 Phase 1a Escalation – Part 1

Subjects in the escalation phase will be enrolled in sequential dose cohorts utilizing the 3 + 3 design shown below starting at Cohort 1. (Cohort 0 represents a contingency de-escalation dose level in the event that tolerance issues are encountered in Cohort 1.)

Cohort	N	Once-weekly Dose
0	3 (+3)	0.01 mg/kg
1	3 (+3)	0.05 mg/kg
2	3 (+3)	0.1 mg/kg
3	3 (+3)	0.3 mg/kg
4	3 (+3)	1 mg/kg

5	3 (+3)	3 mg/kg
6	3 (+3)	10 mg/kg

Each cohort will initially enroll 3 subjects to receive TTI-621 once weekly for 3 weeks. If none of the 3 subjects experience DLT after 3 weeks of dosing and observation, then enrollment in the next cohort may proceed. If 2 or 3 of the 3 subjects experience DLT, then dosing in that cohort will stop and 3 additional subjects will be enrolled at a lower dose (de-escalation). If exactly 1 of the 3 subjects experiences DLT, then an additional 3 subjects will be enrolled in the cohort. If none of the 3 additional subjects experience DLT after 3 weeks of dosing and observation, then enrollment in the next cohort may proceed. If 1 or more of the additional 3 subjects experience DLT, then dosing in that cohort will stop and 3 additional subjects will be enrolled at a lower dose (de-escalation).

Subjects who discontinue the study during the first 3 weeks for reasons other than toxicity or who experience a delay in dosing of more than 3 days for reasons other than DLT will be replaced.

The escalation and de-escalation rules for the escalation phase are summarized in the table below.

Subject Number						
1	2	3	4	5	6	Decision
No subjects have DLT						Escalate
One subject has DLT			No subjects have DLT		Escalate	
			One or more subjects have DLT		De-escalate	
Two subjects have DLT						De-escalate

The highest dose level at which 6 subjects are treated and observed for 3 weeks, with at most 1 subject experiencing DLT, will be declared the MTD.

Subjects may continue to receive TTI-621 after the 3 week DLT observation period until disease progression, unacceptable toxicity, or other reason for treatment discontinuation occurs.

#### Sample Size

The planned sample size is not based on a specific statistical hypothesis but on experience in the conduct of similar trials in subjects with cancer.

For the planned 3+3 dose-escalation design, the probabilities of escalating to the next dose level for a given true rate of DLT are as follows.

True Incidence of DLT	Probability of Escalation
10%	0.91
20%	0.71
30%	0.49
40%	0.31
50%	0.17

60%	0.08
70%	0.03
80%	0.01

Thus, if the true underlying proportion of DLT is low (e.g.,  $\leq 10\%$  at the current dose level, there is a high probability ( $\geq 0.91$ ) of dose escalation to the next dose level. Conversely, if the true underlying proportion of DLT is high (e.g.,  $\geq 60\%$ ) at the current dose level, there is a low probability ( $\leq 0.08$ ) of escalation to the next dose level.

### **1.2.3 Phase 1b Expansion – Part 2**

In the expansion phase, Part 2, subjects with a broader variety of hematologic malignancies and selected solid tumors will be treated at a TTI-621 dose based on the putative optimal dose in order to further define safety, characterize the efficacy, and evaluate the safety of individual subject TTI-621 dose intensification. A cohort of subjects with CD20-positive malignancies will also be enrolled and treated with TTI-621 plus rituximab to characterize the safety and efficacy of the combination. Similarly, a cohort of subjects with classic HL (cHL) will be treated with TTI-621 plus nivolumab to characterize the safety and efficacy of the combination.

The disease cohorts and schedule of treatments administered in the expansion phase Part 2 are summarized in the table below.

	Expansion Cohort	TTI-621 Starting Dose (mg/kg/wk)	Combination Partner Dose
Monotherapy	IBCL (closed)	0.2	NA
	ABCL (closed)	0.2	NA
	TCL (closed)	0.2	NA
	HL (closed)	0.2	NA
	CLL (closed)	0.2	NA
	ALL (closed)	0.2	NA
	MM (closed)	0.2	NA
	AML (closed)	0.2	NA
	MDS (closed)	0.2	NA
	MPN (closed)	0.2	NA
	SCLC (closed)	0.2	NA
Combination Therapy	Rituximab combination: CD20-positive malignancy	0.1	375 mg/m  /wk for up to 8 cycles a
	Nivolumab combination: cHL	0.1	per FDA approved package insert for cHL b

NA: not applicable

a Subjects may continue on TTI-621 monotherapy upon completion of combination partner regimen/unacceptable toxicity to the combination regimen

b Subjects who have unacceptable toxicity to the combination regimen may continue to receive TTI-621 monotherapy

### Sample Size

The planned sample size for each cohort is not based on a specific statistical hypothesis but is based largely on clinical and feasibility considerations in light of the number of distinct cohorts to be evaluated.

In particular, since the primary objective of the expansion phase is to "further characterize the safety of TTI-621 in an expanded number of primary hematologic malignancies and to confirm the optimal dose of TTI-621 that was identified in Phase 1a", then the sample size chosen for each expansion phase cohort is not based on efficacy considerations.

Although the sample sizes for the expansion cohorts are not based on efficacy considerations, it is possible to evaluate the probabilities of observing a specified number of responses (out of 12 subjects) for various hypothesized response rates. These are provided in the table below.

True Response Rate	Probability of Observing Specified Number of Responses (out of 12 subjects)						
	0	$\geq 1$	$\geq 2$	$\geq 3$	$\geq 4$	$\geq 5$	$\geq 6$
10%	0.282	0.72	0.34	0.11	0.03	0.00	0.00
20%	0.069	0.93	0.73	0.44	0.21	0.07	0.02
30%	0.014	0.99	0.91	0.75	0.51	0.28	0.12
40%	0.002	1.00	0.98	0.92	0.77	0.56	0.33
50%	0.000	1.00	1.00	0.98	0.93	0.81	0.61
60%	0.000	1.00	1.00	1.00	0.98	0.94	0.84
70%	0.000	1.00	1.00	1.00	1.00	0.99	0.96
80%	0.000	1.00	1.00	1.00	1.00	1.00	1.00
90%	0.000	1.00	1.00	1.00	1.00	1.00	1.00

For example, the probability of observing no responses is low (0.002=0.2%) when the true response rate is 40%. Similarly, the probability of observing 3 or more responses is high (0.92=92%) when the true response rate is 40%. When the true response rate is only 10%, the probability of observing 3 or more responses is 11%.

The ability to draw statistical conclusions about response rates in a cohort of size 12 is limited. This is illustrated by the following table of 95% confidence intervals (CIs) for various numbers of responding subjects.

Number of Responders	Observed Response Rate	95% CI 
0	0%	(0%, 26%)
1	8%	(0%, 38%)
2	17%	(2%, 48%)
3	25%	(5%, 57%)
4	33%	(10%, 65%)
5	42%	(15%, 72%)
6	50%	(21%, 79%)
7	58%	(28%, 85%)

8	67%	(35%, 90%)
9	75%	(43%, 95%)
10	83%	(52%, 98%)
11	92%	(62%, 100%)
12	100%	(74%, 100%)

 Confidence intervals have been calculated using the Clopper-Pearson method.

For the Phase 1b portion (Part 2) of the study, the cohort size for selected cohorts has been increased to 40 subjects. This is to improve the precision of the overall response rate (ORR) estimate. For example, for an ORR of 30%, in 10 subjects, the lower confidence limit (LCL) of a 95% one-sided confidence interval is 8.7%, or a distance of 21.3% (30-8.7) from the ORR. When the sample size is increased to 40 for the same ORR, the LCL is 18.3%, or a distance of 11.7% (30-18.3) from the ORR. This anticipated improvement in the precision of the point estimate will be particularly important given the relative heterogeneity of the enrolled population.

#### **1.2.4 Phase 1b Dose Expansion – Part 3**

In the expansion phase, Part 3, based upon preliminary observations of response, 2 cohorts (subjects with CTCL and PTCL), will be evaluated separately, using the Simon 2-stage design, for the potential to be further studied. Dose intensification was required for all newly enrolled subjects starting at Week 3, in 0.1 mg/kg weekly increments, to a maximum of 0.5 mg/kg/week (see Protocol Section 6.5.4 for details).

The disease cohorts and schedule of treatments administered in the expansion phase Part 3 are summarized in the table below.

	Expansion Cohort	TTI-621 Starting Dose (mg/kg/wk)	Combination Partner Dose
Monotherapy	CTCL	0.2	NA
	PTCL	0.2	NA

NA: not applicable

#### Sample Size

For the Phase 1b (Part 3) expansion cohorts for CTCL and PTCL, the cohort size has been selected based upon a Simon optimal 2-stage design, with the low and high boundaries of the response rate being 10% (not effective) and 30% (warrants further study) respectively, and a power of 90% and an alpha of 0.05. The calculations were performed using PASS 14 (NCSS, 2015) and the Optimum design chosen. The total sample size is 35 subjects per cohort under the scenario described below. For the first stage, a total of 18 subjects will be enrolled in each cohort. At the end of Stage 1, if 2 or fewer responders are observed per cohort, enrollment in this cohort will be terminated, otherwise, enrollment will proceed to the second stage and an additional 17 subjects will be enrolled per cohort for a total of 35 subjects per cohort. At the end of the second stage, if 6 or fewer responders are observed per

cohort, the drug will be rejected for further testing in this indication. The probability of early termination (PET) = 0.734 at the end of the first stage if the true response rate is less than 10%.

N1	R1	PET	N	R	Average N	Alpha	Beta
18	2	0.734	35	6	22.53	0.047	0.098

### **1.2.5 Phase 1b Dose Optimization – Part 4**

In the dose optimization phase, Part 4, the safety and tolerability of TTI-621 at higher dose levels beyond the initially recommended Phase 1b dose of 0.2 mg/kg (as determined during Phase 1a dose escalation) and the highest dose of TTI-621 evaluated (0.5 mg/kg) during Phase 1b dose expansion following dose intensification permissible per protocol, will be evaluated. This Phase 1b dose optimization phase will aim at re-defining MTD following 3+3 dose escalation schema and a revised DLT criteria based on the totality of safety data collected thus far from Phase 1a and 1b dose expansion phase of the study. In Phase 1b dose optimization of the study (Part 4), further dose escalation of TTI-621 will be pursued in subjects with relapsed and/or refractory CTCL following a 3+3 escalation design and using a revised DLT criteria. Dose optimization will proceed following review of the data obtained from the Phase 1b Part 3, stage 1 cohorts of CTCL and PTCL subjects. Alternative dosing schedules, intermediate doses, and other optimization options may be considered by the SRC following review of available data.

Part 4 Q2W is an expansion to Part 4 Cohort 5 (P4-5). Dosing is done at the 2.0 mg/kg dose level and explores a TTI-621 biweekly (every other week) dosing schedule.

#### Sample Size

Up to 6 DLT evaluable subjects may be enrolled at each dose level evaluated during the escalation phase. The number of subjects enrolled at each dose level and the dose-step increments between adjacent dose levels will be based on a 3 + 3 dose escalation scheme (protocol Section 3.2.2). Once the MTD or a recommended dose is estimated (with the required six DLT-evaluable subjects at that dose level), an additional six subjects will be treated at that dose level (for a total of twelve subjects). These additional subjects will allow further examination of the safety and tolerability of the dose and a preliminary examination of the efficacy of the dose. With twelve subjects, if the observed response rate is 33%, the lower bound of a two-sided 90% confidence interval would be 0.12. The maximum width of the 90% CI would be 0.51.

We expect to accrue approximately 25 subjects in Part 4. The actual number required will depend upon the observed safety profile, which will determine the number of subjects per dose level, as well as the number of dose escalations required to achieve the MTD or the recommended dose.

### **1.2.6 Timing of Analysis Reporting**

Separate sets of tables, figures, and listings (TFLs) will be produced for Phase 1a and for each of the Phase 1b parts. Regular interim reviews of safety data will be held during the escalation phase, but no interim analyses for efficacy are planned for

either Phase 1a or Phase 1b parts. A single Clinical Study Report will be written after enrollment and follow-up is complete for the study.

### **1.2.7 Responsibilities**

Activities related to the development, approval, and maintenance of the SAP (sans specified portions provided by Pfizer Inc.), along with applicable study analysis and reporting will be the responsibility of assigned Sarah Cannon Development Innovations study team members. After completion of the final CSR, all applicable datasets, outputs, programs, and specification documents, including interim safety reviews, will be transferred to the Sponsor for archiving.

## **2 Analysis Populations**

The analysis of data will focus on the following analysis sets.

### Safety Analysis Set

The Safety Analysis Set is the primary population for analyses of safety data and consists of all subjects who receive at least 1 dose of study treatment.

### DLT-evaluable set (for Part 1 and non-Q2W Part 4 only)

The DLT-evaluable set consists of 1) subjects who have received all 3 doses within the DLT evaluation period, OR 2) subjects who experienced an adverse event (AE) meeting DLT criteria during that time. Those who drop out of the study during the DLT evaluation period for reasons other than toxicity or who experience a delay in dosing of more than 3 days for reasons other than DLT are considered unevaluable for DLT.

The DLT evaluation period consists of the first 21 days on study for subjects initially assigned to Part 1 and non-Q2W Part 4. For subjects who experienced a treatment delay, the DLT observation period will extend 7 days beyond the third dose of TTI-621.

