## 1.7 Anticipated or Possible Risks in Human Subjects

### *Summary of Dose-Escalation Safety Data*

Data from the first 18 subjects enrolled in the dose-escalation phase of the study show that TTI-621 has been reasonably well tolerated. Transient, dose-dependent decreases in platelets without clinical sequelae occurred in the hours following infusion in the majority of subjects exposed to TTI-621. Thrombocytopenia was relatively brief with recovery to baseline platelet counts by the next weekly dose and appeared attenuated with weekly TTI-621 exposure. Other Grade 3/4 cytopenias (monocytes, neutrophils, and lymphocytes) were also frequently observed; all were transient and resolved without sequelae.

The majority of subjects experienced mild to moderate infusion-related reactions (IRRs) that typically occurred after the first TTI-621 infusion only. IRRs were reported across all dose cohorts with no obvious dose relationship and occurred despite premedication with an antihistamine and acetaminophen.

Three subjects experienced reversible Grade 3 hypophosphatemia in the days following their first infusion of TTI-621. Hypophosphatemia in 1 of the 3 subjects was considered related to TTI-621 and was therefore reported as a DLT. The event rapidly resolved without intervention. Hypophosphatemia was considered unrelated to TTI-621 in the other 2 subjects and their phosphate levels were corrected by oral phosphate.

No subjects in either the 0.05 mg/kg/week or 0.1 mg/kg/week dose groups experienced dose-limiting toxicity (DLT). However DLTs were reported for 2 of 5 subjects treated at the 0.3 mg/kg/week dose: 1 subject with Grade 4 thrombocytopenia and 1 subject with Grade 4 thrombocytopenia and Grade 3 elevated alanine aminotransferase/aspartate aminotransferase (ALT/AST). Upon review of cumulative adverse events (AEs) and laboratory values, the Safety Review Committee (SRC) recommended proceeding with

enrollment at an intermediate dose level of 0.2 mg/kg TTI-621 (Cohort 2a), and to dose reduce all subjects participating in the 0.3 mg/kg cohort to the 0.2 mg/kg dose level (one subject was dose reduced to the 0.1 mg/kg dose level).

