### 3.3.2 Phase 1b Dose Optimization Part 4 (to be enrolled as of Amendment 9)

A minimum of 3 patients will be treated in each cohort sequentially in a 3 + 3 design. The planned dose escalation levels are shown in [Table 3-4](#). Patients will receive once weekly dosing of TTI-621 at the dose levels in their assigned cohort regimen (Week 1 given on Day 1, Week 2 given on Day 8, and Week 3 given on Day 15). The DLT observation period is 21 days. Patients will be considered evaluable for DLT if they receive all 3 weekly doses within the DLT evaluation period or if they experience an AE meeting DLT criteria during that time. If a patient experiences a non-DLT event that requires a dose to be held per dose modification guideline ([Section 6.5](#)), the DLT evaluation period can be extended to 28 days. If a DLT occurs in 1 of 3 patients within a cohort, 3 additional patients will be treated at that cohort regimen. In the absence of DLT, enrollment will proceed sequentially through the planned dose levels.

Alternative dose escalation including evaluation of intermediate doses, expansion of an existing dose level, evaluation of alternative regimens/schedules including a dose ramp-up design following different dose intensification increments and schedule, and modification of dosing frequency and/or IV infusion rate are all permissible if supported by the evolving data and a SRC decision. All patients in each cohort must have completed the 21-day DLT period before the next cohort begins treatment. The MTD of TTI-621 will be the dose below the one in which  $\geq 2$  DLTs are observed among 6 treated patients.

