
Grade 3 or greater non-hematologic toxicity related to TTI-621 with the following exceptions:
 
 
• Grade 3 nausea and/or vomiting lasting <72 hours with standard supportive care
 
• Transient Grade 3 fatigue lasting <math>\leq</math>72 hours
 
• Transient asymptomatic Grade 3 laboratory abnormalities that last <72 hours with standard supportive care and considered not clinically significant following agreement between investigators and the sponsor or designees.
 
	
For Grade 3 events, delay TTI-621 dosing until the re-treatment criteria is met, then resume TTI-621 at a reduced dose by 1 dose level.
 
No dose reduction is required for the exceptions listed.
 
For Grade 4 events, discontinuation of TTI-621 should be considered. If, per investigator's assessment, it is in the patient's best interest to continue the treatment, TTI-621 treatment can be resumed when the AE resolves to a level that meets the re-treatment criteria
 
Do not intensify dose (Part 3)

Grade 3 or greater non-hematologic toxicity NOT related to TTI-621	Investigator's discretion to withhold or decrease dose of TTI-621. Do not intensify dose of TTI-621 until the resolution of the AEs to Grade 1, baseline, or a level (must be $\leq$ Grade 2) determined to be acceptable per investigator assessment (Part 3)

Grade 3 anemia	
Delay TTI-621 dosing until resolution to <math>\leq</math> Grade 1 or baseline, then resume TTI-621 treatment:
 
 
• at the same dose if dose delay for 1 week;
 
• at a reduced dose by 1 dose level if dose delay for <math>> 1</math> week;
 
• at a reduced dose by 1 dose level if the event recurs
 
• Dose intensification can occur only when there is no occurrence of the same event upon re-dosing of TTI-621 at the same dose for two consecutive weeks. When dose reduction occurs, no further dose intensification will be allowed (Part 3).
 

Grade 4 anemia	
Discontinuation of TTI-622 should be considered. If it is in the patient's best interest to continue TTI-622 per investigator assessment, withhold dose until resolved to <math>\leq</math> Grade 1 or baseline, then reduce by 1 dose level.

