#### 6.6 Intra-patient Dose Reduction and Escalation (Phase 1b Dose Optimization Part 4: DLT evaluation period)

Intra-patient dose reductions of TTI-621 are not permitted in the DLT evaluation period (Week 1-3) in the phase 1b dose optimization unless the patient experiences a DLT attributed to TTI-621. If a patient experiences a DLT during the first 21 days, treatment should be held and the event counted toward the assessment of MTD for the given cohort. These patients may continue in the study upon resolution of the toxicity at a reduced dose

level. Patients who receive a reduced dose of TTI-621 during the DLT evaluation period for reasons other than DLT will be replaced.

During phase 1b dose optimization, when the MTD or recommended phase 2 dose of TTI-621 is determined, all patients who have received TTI-621 at a dose lower than the recommended dose for a minimum of 4 weeks may dose escalate to the recommended dose in the absence of PD or unacceptable treatment-related toxicity at the investigator's discretion and with the medical monitor's approval. Patients for whom an increase in the dose of TTI-621 is being considered must have TEAEs resolve to  $\leq$ Grade 1 or baseline or to a level that is acceptable to the investigator (non-hematologic toxicity must be  $\leq$ Grade 2, hematologic toxicities must be recovered to levels above the minimum requirement for TTI-621 dosing).

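### For non-Q2W Part 4, the DLT-evaluable definition keeps patients whom Protocol 6.6 replaces after a dose reduction not caused by a DLT

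*SAP*

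**What the plan says.** **SAP section 2, DLT-evaluable set (Part 1 and non-Q2W Part 4).** The first route into the set reads: "The DLT-evaluable set consists of 1) subjects who have received all 3 doses within the DLT evaluation period". The second route is an adverse event meeting DLT criteria in the window. Two groups are excluded: those who drop out for reasons other than toxicity, and those "who experience a delay in dosing of more than 3 days for reasons other than DLT are considered unevaluable for DLT". Dose reduction is not mentioned.

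**Protocol 3.3.2 (Part 4).** "Patients will be considered evaluable for DLT if they receive all 3 weekly doses within the DLT evaluation period", or if they have a DLT. This sentence is also silent on the dose given.

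**Protocol 6.6 (Part 4, DLT evaluation period).** Reductions in Weeks 1 to 3 are barred unless the patient has a DLT. The section then says what follows if one happens anyway: "Patients who receive a reduced dose of TTI-621 during the DLT evaluation period for reasons other than DLT will be replaced".

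**Use of the set.** SAP 1.2.5 describes naming an MTD or recommended dose "with the required six DLT-evaluable subjects at that dose level", and Protocol 8.3 has the same requirement. SAP section 3 summarises Part 4 by initial assigned dose level. SAP 3.1 counts the DLT-evaluable set in the disposition table. SAP 3.5 names the Safety Analysis Set as the population for safety, and the DLT summary in 3.5.1 falls under it.

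**The concern.** A patient is replaced because the observation does not inform the assigned dose level. In Part 1 the two ideas go together: Protocol 3.2.1 treats its drop-outs and delayed subjects as unevaluable and replaces them. The SAP applies that Part 1 exclusion wording to Part 4 but leaves out the replacement reason that Protocol 6.6 adds for Part 4. Protocol 3.3.2 does not refer to 6.6 either, so the protocol is inconsistent with itself.

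At stake is the count of DLT-evaluable subjects that supports the Part 4 MTD or recommended dose. DLT is a primary endpoint for Part 4 in SAP 1.1.3. If criterion 1 is applied as written, a level can be reported with six evaluable subjects when only five were observed at its dose, and the under-dosed patient appears as DLT-free at the higher level.

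**Working it through.** The point is a conflict of definitions. The documents state no Part 4 DLT count or rate to reproduce.

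**Step 1. Follow one patient through each rule.** Take a Part 4 patient dosed on Days 1, 8 and 15, with dose 2 or dose 3 reduced for an event that is not a DLT, and no delay.

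| Rule | Result |
|---|---|
| SAP section 2, criterion 1 | Met: three doses in the window |
| SAP section 2, drop-out exclusion | Does not apply |
| SAP section 2, delay exclusion (more than 3 days) | Does not apply |
| Protocol 3.3.2 | Evaluable |
| Protocol 6.6 | Replaced |
| SAP section 3, grouping | Shown at the initial assigned level |

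The SAP and Protocol 3.3.2 keep this patient as evaluable without a DLT. Protocol 6.6 replaces the same patient.

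**Step 2. Who can be affected.**
- Related non-hematologic toxicity of Grade 2 or higher that the investigator judges to need a reduction is itself a DLT (Protocol 3.3.3, SAP 1.1.3). These patients enter by the second route.
- A reduction that follows a non-DLT delay of more than 3 days is removed by the SAP's delay exclusion.
- What remains is an on-schedule reduction for another reason. Table 6-1 gives one setting, Grade 3 or greater non-hematologic toxicity not related to study drug: "Investigator's discretion to withhold or decrease dose of TTI-621". Section 6.5 applies except where otherwise noted, and 6.6 bars non-DLT reductions in Weeks 1 to 3, so using this option in the window would be a deviation.

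**Step 3. Size, by illustration.** Assume one DLT at the level and one patient with an on-schedule non-DLT reduction. Rate = x/n. The exact 95% limits are the 2.5% quantile of Beta(x, n − x + 1) and the 97.5% quantile of Beta(x + 1, n − x). As a check on the method, the same interval at 90% for 4/12 gives a lower bound of 0.123 and a maximum width for n = 12 of 0.509, matching the 0.12 and 0.51 in SAP 1.2.5.

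| Situation | Reduced patient excluded | Reduced patient kept |
|---|---|---|
| Replacement not yet enrolled | 1/5 = 20.0% (0.5% to 71.6%) | 1/6 = 16.7% (0.4% to 64.1%) |
| Replacement enrolled | 1/6 = 16.7% (0.4% to 64.1%) | 1/7 = 14.3% (0.4% to 57.9%) |

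The differences are 1/5 − 1/6 = 1/30, or 3.3 percentage points, and 1/6 − 1/7 = 1/42, or 2.4 points. In the first row, whether the patient is kept also decides whether the level has the required six evaluable subjects or only five.

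**The case against.** The strongest reply is that this will seldom arise and that the protocol already corrects it. Section 6.6 forbids the reduction, most reductions for related toxicity come with a DLT or a long delay, and a replaced patient is followed by a new one, so the level ends with six full-dose patients plus one. Most of that stands. The group is narrow, and the level falls short of six only if the reduced patient is counted before, or instead of, the replacement. It does not remove the conflict: 6.6 itself provides for such patients, and the SAP and Protocol 3.3.2 classify them differently.

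A reader might infer three stronger things that the documents do not support.

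- **That the SAP set makes escalation more likely.** The 3+3 rule passes a level with probability (1−p)³ + 3p(1−p)²(1−p)³. At p = 0.40 this is 0.309, the 0.31 in SAP 1.2.2. If one of the first three subjects is counted but carries an assumed DLT risk of 20% to 0%, it becomes 0.386 to 0.464. That is not an effect of the SAP definition. The SRC makes the live decisions under the protocol, where 6.6 applies, and SAP version 2.0 (November 2022) covers analyses for the abbreviated study report. A patient reduced at dose 2 or 3 has also had at least one full dose, so the lowest assumed risks are extreme.
- **That Part 1 is affected.** The SAP set covers Part 1, but Protocol 3.2.1 and SAP 1.2.2 replace subjects there only for drop-out or a delay of more than 3 days. The SRC recommendation "to dose reduce all subjects participating in the 0.3 mg/kg cohort to the 0.2 mg/kg dose level" came after two DLTs at that level, so it is not clearly a reduction for another reason. Two DLTs already fail the level under Table 3-2.
- **That the reported DLT rate is biased downward.** The SAP ties no DLT rate to the DLT-evaluable set. Its DLT summary falls under the Safety Analysis Set, which would keep these patients whatever criterion 1 says.

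**Conclusion.** The point holds for non-Q2W Part 4 only. SAP section 2 and Protocol 3.3.2 classify as DLT-evaluable a patient whom Protocol 6.6 replaces, and the SAP shows that patient as DLT-free at the initial assigned level. The consequence lies in how the evaluable count and the support for the MTD or recommended dose are reported.

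The actual effect cannot be sized, because no document says whether any such patient exists. Under the assumption of one DLT and one such patient, the shift is 20.0% to 16.7%, or 16.7% to 14.3% once the replacement is enrolled. Both shifts are small beside the exact intervals. The more material risk is a level credited with six evaluable subjects when it has five. The correction should be made because the conflict is plain and cheap to remove.

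**What to change.** Reconcile SAP section 2 and Protocol 3.3.2 with Protocol 6.6:

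1. In both places state that, for Part 4, the first criterion requires all three doses at the level or levels assigned to the cohort, including any priming dose. The priming wording matters because Protocol Table 3-4 assigns a lower Week 1 dose in a priming regimen, and those patients must not be dropped.
2. Add that Part 4 patients whose dose is reduced in the window for a reason other than DLT are not DLT-evaluable, citing Protocol 6.6. Leave the second criterion as it is, so that every patient with a DLT is kept.
3. In SAP 3.5 or 3.5.1 name the DLT-evaluable set as the denominator for the Part 4 DLT summary. Without this, the change to section 2 would not reach that table.

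The Part 1 definition stays as it is, and no dosing rule changes. The cost is one clause in each document and one sentence on the denominator. The data exist, since SAP 3.4 already identifies dose reductions from the treatment CRF. The downside is that a cohort may show one fewer evaluable subject.
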